#### Document History

Document instory			
Version Date	Summary of Changes		
18-August-2017	Not applicable (N/A)		
	Version Date 18-August-2017		

Amendments incorporate all revisions to date, including amendments made at the request of country health authorities, independent ethics committee (EC), etc.

# SCHEDULE OF ACTIVITIES

The schedule of activities table provides an overview of the protocol visits and procedures.

The investigator may schedule visits (unplanned visits) in addition to those listed on the schedule of activities, in order to conduct evaluations or assessments required to protect the well-being of the subject.

Table 1-1	Schedule of Activities
-----------	------------------------

Procedure/Assessment			Study Period		End of Treatment	
	Visit 1		Visit 2 Day 1 Baseline	Visit 3 Day 29±3	Visit 4 Day 57±3	
Informed consent	Х					
Demographics, Ethnicity	Х					
Medical History, Current Medications	Х					
Concomitant Medications			Х	Х	Х	
Review of Subjects Current Oral Care Products to Confirm They Don't Contain any Anti-sensitivity Ingredients	х					
Urine Pregnancy Test in Female Subjects of Childbearing Potential		sks	х			
OST Examination	Х	We	Х	Х	Х	
OHT Examination	Х	2-6 weeks				
Eligible Teeth Assessments (Dentition Exclusions, EAR, MGI, Tooth Mobility)	х	period				
Qualifying Tactile Assessment (Yeaple Probe) 	Х	uo				
Qualifying Evaporative Air Sensitivity (Schiff Sensitivity Score) 	Х	Acclimatization				
Inclusion/Exclusion Criteria	Х	mat	X 			
Subject Eligibility	Х	ccli	Х			
Dispense Acclimatization Dentifrice, Toothbrush, Diary and Timer 	х	∢				
Supervised Brushing with Acclimatization Dentifrice 	Х					
Return Acclimatization Dentifrice, Toothbrush, Diary			Х			
Subject Adherence and Continuance			Х	Х	Х	
Tactile Assessment (Yeaple Probe) 			Х	Х	Х	
Evaporative Air Assessment (Schiff Sensitivity Score) 			Х	Х	Х	
Identify Two Test Teeth			Х			
Stratification and Randomization			Х			
Dispense Randomized Dentifrice, Toothbrush, Diary and Timer 	ense Randomized Dentifrice, Toothbrush, Diary and Timer  X X					
Supervised Brushing with Allocated Dentifrice 			Х	Х		
Subjects Return Study Supplies to Site				Х	Х	

GlaxoSmithKline Consumer Healthcare Confidential Template Version Effective: 22-Jun-2017

Page 8 of 60

Document Name	208153 Clinical Protocol.docx		
Туре	Version	Document Identifier	Effective Date
eldo clinical doc	3.0; Most-Recent; Effective; CURRENT	090032d580d852b1	3-Aug-2017 05:58:20
Reason For Issue	Auto Issue		0

Stannous fluoride

Protocol Number 208153 Final 1 0 Clinical Protocol

Final 1.0 Chinical Protocol					
Procedure/Assessment	Screening	zalio 2-6	Study Period		End of Treatment
	Visit 1	period	Visit 2 Day 1 Baseline	Visit 3 Day 29±3	Visit 4 Day 57±3
Visual Compliance Check of Returned Study Dentifrice and Review of Subject Diary			х	х	х
Adverse Events 	Х		Х	Х	Х
Study Conclusion					Х

Abbreviations: OST = Oral Soft Tissue; OHT = Oral Hard Tissue; EAR = Erosion, Abrasion, Recession; MGI = Modified Gingival Index.

- Qualifying Schiff sensitivity and tactile threshold scores will be recorded in the case report form (CRF). Evaporative air assessment to
  follow tactile assessment; minimum 5 minutes time lapse between the two assessment types for tooth recovery. At Screening,
  maximum force for tactile = 20g.
- 2. Inclusion criteria 6d and exclusion criteria 13b.
- 3. Subject is instructed to bring all supplies back to next visit.
- 4. Study supplies to be returned to subject (for use at home) after supervised brushing.
- 5. At Baseline, maximum force = 20g., at all subsequent visits maximum force = 80g.
- 6. Evaporative air assessment to follow tactile assessment; minimum 5 minutes time lapse between the two assessment types for tooth recovery.
- Subject is instructed to bring all supplies back to subsequent visits for compliance checks. Study supplies to be returned to subject after supervised brushing. At the Week 4 visit subjects will be re-dispensed with a new diary and new tubes of their allocated dentifrice prior to conducting their supervised brushing.
- 8. Any serious adverse event assessed as related to study participation that occurs subsequent to the signing of informed consent and any adverse event that occurs subsequent to the first dose of the acclimatization dentifrice will be recorded.

GlaxoSmithKline Consumer Healthcare Confidential Template Version Effective: 22-Jun-2017 Page 9 of 60

# 1 INTRODUCTION

Dentine hypersensitivity (DH) has been defined as 'pain derived from exposed dentine in response to chemical, thermal, tactile, or osmotic stimuli which can't be explained as arising from any other dental defect or disease' [Addy, 1985; Canadian Advisory Board on Dentin Hypersensitivity, 2003]. The primary aetiological factors associated with the onset of DH include gingival recession and/or enamel loss (e.g. through erosion or abrasion) that result in exposure of dentine with patent dentinal tubules [Orchardson, 1987]. The hydrodynamic theory of DH hypothesises that a stimulus external to the tooth (e.g. a temperature/osmotic differential) causes transport of the fluid resident within dentinal tubules [Brännström, 1962]. This fluid movement may stimulate nerve processes in the pulpal area of the dentine including irritation of odontoblasts, pulpal neurons, and even subodontonblastic blood vessels [Hall, 2000], resulting in the characteristic short, sharp pain of DH.

Currently there are two approaches to the management of DH: either nerve depolarization or dentinal tubule occlusion. Nerve depolarising agents, typically potassium salts, generally require a period of use (for example, 14 to 28 days) before their benefit is established. The delivery of potassium ions to the dentine-pulp junction (odontoblastic layer) *via* dentinal tubules is believed to result in depolarisation of the afferent nerve membrane thereby blocking the pain response [Orchardson, 2000]. The second approach uses tubule occluding agents which physically block the exposed end of the dentinal tubules, thus reducing dentinal fluid movement and pulpal irritation. Tubule occluding agents, like stannous salts, serve to seal or block the dentine tubules and thereby reduce the effect of external stimuli. Such agents are believed to function by precipitating insoluble materials onto the dentine surface and/or within the dentinal tubules to reduce dentinal fluid transport [Pashley, 1986].

Stannous fluoride  $(SnF_2)$  has been incorporated into oral hygiene products indicated for the reduction of DH since the 1960's [Schiff, 2006]. SnF2 provides relief from DH by the occlusion of the dentinal tubules through chemical precipitation of stannous oxides and hydroxides onto the surface of the dentine. More recently Proctor and Gamble (P&G) and GSK CH have marketed SnF2-containing dentifrices indicated for DH relief, with published evidence demonstrating longitudinal clinical efficacy [Ni, 2011; Parkinson, 2011; Makin, 2013]. In this study the efficacy of an experimental formulation containing 0.454% w/w SnF2 will be compared to a negative control dentifrice and a Chinese marketed positive control dentifrice (Crest 7-Effects Strengthen Dental Enamel) for the relief of DH pain.

# 1.1 Mechanism of Action/Indication

Stannous fluoride is a dentine tubule occluding agent that is being investigated in subjects with DH. Such agents are believed to function by precipitating insoluble materials onto the dentine surface and/or within the dentinal tubules to reduce dentinal fluid transport [Pashley, 1986].

GlaxoSmithKline Consumer Healthcare Confidential Template Version Effective: 22-Jun-2017 Page **10** of **60** 

Final 1.0 Clinical Protocol

## 1.2 Background and Rationale

#### 1.2.1 Justification on the Requirement to Conduct the Study

A similarly designed randomized, examiner-blind, two treatment arm parallel group DH study was previously conducted in a Chinese population [GSK CH Study 205794]. The results of this study demonstrated a statistically significant reduction in DH for Schiff sensitivity score for the experimental product containing  $SnF_2$  compared to a regular fluoride dentifrice, but failed to demonstrate a statistically significant greater reduction in tactile threshold. Given that a number of successful 8 week DH studies have been conducted on  $SnF_2$  containing dentifrices by GSK CH and competitors, there is a need to repeat this study in a Chinese population to demonstrate statistically significant improvements in both sensitivity measures that meet the Chinese Ministry of Health guidelines [Ministry of Health (China), 2010].

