• To compare the clinical efficacy of positive control dentifrice for the relief o DH, as elicited by an evaporative ai stimulus (with Schiff sensitivity score against a negative control dentifrice when used twice daily for 4 and 8 weeks	f sensitivity score at 4 and 8 weeks r )	
Safety		
• To evaluate the safety and ora tolerability of the test dentifrices when used twice daily for 8 weeks.		

This study will be considered successful if there is a statistically significant difference in the primary efficacy variable, change from baseline in Schiff sensitivity score, after 8 weeks of treatment. The difference should be viewed as clinically relevant in addition to being statistically significant

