#### 10.2.10 Other Analyses

To cover the Chinese requirement to demonstrate a 15% difference between the Test Product and Control product 1, the difference between treatments in the raw means of the actual score (note not change from baseline) will be calculated and presented. This will be done for Schiff and tactile at weeks 4 and 8. The calculation is: -

100\*(Test-Ref 1)/Ref 1

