## 1 Summary of Key Protocol Information

The purpose of this trial is to demonstrate the efficacy and safety of a experimental 0.454% weight/weight (w/w) Stannous fluoride (SnF2) dentifrice to treat the symptoms of Dental Hypersensitivity (DH). Efficacy will be demonstrated as a treatment difference in favour of the 0.454% w/w SnF2 dentifrice versus the Negative Control dentifrice for the primary efficacy outcome, Schiff sensitivity score at Week 8. Safety will be demonstrated through assessment of adverse events (AEs).

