#### 4.8 Analysis of Other Variables

To cover the Chinese Ministry of Health guideline requirement, to demonstrate at least a 15% difference between the Test Product and Negative Control, the difference between treatments in the raw means of the actual score (note: not change from baseline) will be calculated using below formula for Schiff sensitivity and tactile threshold at Weeks 4 and 8 (Table 14.2.1.1 and 14.2.2.1).

$$100 * (\text{Test Product} - \text{Negative Control Product}) / \text{Negative Control Product}$$

Similar difference will be calculated between Test product and Positive Control.

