[1] From ANCOVA model with treatment as factor and baseline Schiff score as covariate. Difference is first named treatment minus second named treatment such that a negative difference favors the first named treatment.

[2] For the Chinese Ministry of Health guideline requirement to demonstrate difference between Test Product and Control (Positive or Negative) in the observed raw means. It is Calculated as  $100 * (\text{Test Product} - \text{Control}) / \text{Control}$ .

Page x of y

PPD

GlaxoSmithKline Consumer Healthcare Confidential

Stannous Fluoride (SnF2)

208153

Final Statistical Reporting and Analysis plan V1.0 14 Dec 2017

*Programming Note: For Table 14.2.2.2 and 14.2.2.4: please update footnote [1] as  
[1] From ANCOVA model with treatment and baseline Schiff stratification as factors and baseline tactile threshold as a covariate. Difference is the first named  
treatment minus second named treatment such that a positive difference favors the first named treatment.*

Stannous Fluoride (SnF2)

208153

Final Statistical Reporting and Analysis plan V1.0 14 Dec 2017

Protocol 208153

Program Run Date:xxxx

Table 14.3.1.1  
Treatment Emergent Adverse Event by SOC and Preferred Term  
Safety Population

Study Population: Safety Population (N=xx)

SOC Preferred Term	Test Product (N=XX)		Negative Control (N=XX)		Positive Control (N=XX)		Overall (N=XX)	
	n (%)	nAE	n (%)	nAE	n (%)	nAE	n (%)	nAE
NUMBER OF SUBJECTS WITH AT LEAST ONE AE	xx (xx.x)	xx	xx (xx.x)	xx	xx (xx.x)	xx	xx (xx.x)	xx
NUMBER OF SUBJECTS WITH NO AE	xx (xx.x)	xx	xx (xx.x)	xx	xx (xx.x)	xx	xx (xx.x)	xx
SKIN AND SUBCUTANEOUS TISSUE DISORDERS	xx (xx.x)	xx	xx (xx.x)	xx	xx (xx.x)	xx	xx (xx.x)	xx
ERYTHEMA	xx (xx.x)	xx	xx (xx.x)	xx	xx (xx.x)	xx	xx (xx.x)	xx
DERMATITIS	xx (xx.x)	xx	xx (xx.x)	xx	xx (xx.x)	xx	xx (xx.x)	xx
GASTROINTESTINAL SYSTEM	xx (xx.x)	xx	xx (xx.x)	xx	xx (xx.x)	xx	xx (xx.x)	xx
ABDOMINAL PAIN	xx (xx.x)	xx	xx (xx.x)	xx	xx (xx.x)	xx	xx (xx.x)	xx
DRY MOUTH	xx (xx.x)	xx	xx (xx.x)	xx	xx (xx.x)	xx	xx (xx.x)	xx
VOMITTING	xx (xx.x)	xx	xx (xx.x)	xx	xx (xx.x)	xx	xx (xx.x)	xx

Etc.

n (%) = Number (percent) of subjects nAE = Number of adverse events.

Page x of y

PPD

Stannous Fluoride (SnF2)

208153

Final Statistical Reporting and Analysis plan V1.0 14 Dec 2017

Protocol 208153

Program Run Date:xxxx

Listing 16.1.7  
Randomization Information  
Randomized Population

Study Population: Randomized (N=xx)  
Stratum 1: Maximum Schiff score =2

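### Does the success rule need a numerical criterion for clinical relevance, and the guideline's 15% difference a pass rule?

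*Protocol*

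**What the plan says.** **Purpose.** Protocol Section 1.2.1 reports that the earlier study, 205794, succeeded on Schiff but not on tactile, and that a repeat is needed "to demonstrate statistically significant improvements in both sensitivity measures that meet the Chinese Ministry of Health guidelines".

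**Success rule.** Protocol Section 2: "This study will be considered successful if there is a statistically significant difference in the primary efficacy variable", at 8 weeks. It then adds: "The difference should be viewed as clinically relevant in addition to being statistically significant". No threshold or assessor for relevance is named. SAP Section 1 puts it more briefly: "Efficacy will be demonstrated as a treatment difference in favour of the 0.454% w/w" dentifrice over Negative Control on Week 8 Schiff, without mentioning relevance.

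**The 15% figure.** Protocol Section 10.2.10 introduces a percentage difference in raw means: "To cover the Chinese requirement to demonstrate a 15% difference between the Test Product and Control product 1". On scope it says: "This will be done for Schiff and tactile at weeks 4 and 8". SAP Section 4.8 gives the purpose as "to demonstrate at least a 15% difference between the Test Product and Negative Control". The shell of SAP Table 14.2.1.2 carries the percentage with the footnote "For the Chinese Ministry of Health guideline requirement to demonstrate difference between Test Product and Control (Positive or Negative) in the observed raw means", and shows no confidence interval for it.

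**Tests.** Schiff at Week 8, Test versus Negative Control, is the single primary comparison (Protocol 10.2.2, SAP 4.4.1.2). Tactile at Week 8, same comparison, is the single secondary one (Protocol 10.2.3, SAP 4.5.1). Protocol 10.1 gives 80% power with 55 evaluable subjects per group, a difference of 0.33 and SD 0.619, by a two-sided 5% t-test.

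**The concern.** Three things look loose when these sections are read together.

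1. Success has a second limb, clinical relevance, with no criterion. The 0.33 in Section 10.1 is a power input and is not described as a relevant difference.
2. Both documents speak of the 15% as something to be demonstrated, yet they only calculate it. There are four results against Negative Control (two measures, two visits). Nothing says which must reach 15%, whether a point estimate is enough, or what follows a miss. The threshold carries no sign, although by the formula benefit is negative for Schiff and positive for tactile.
3. The purpose names two measures and the success rule names one. A repeat of the 205794 pattern would still satisfy the statistical limb.

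If a significant Schiff result fell below 15%, the sponsor might have to decide afterwards whether the study had succeeded.

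**Working it through.** **Step 1. The plan's power figure.** Inputs from Protocol 10.1: n = 55 per arm, difference 0.33, SD 0.619, two-sided 5%.

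- SE = 0.619 × √(2/55) = 0.1180
- Noncentrality = 0.33 / 0.1180 = 2.80; power from the noncentral t on 108 degrees of freedom = 79.1% (79.8% by the normal approximation)

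The stated 80% reproduces.

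**Step 2. Where significance and 15% part company.**

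- Smallest significant difference = 1.982 × 0.1180 = 0.234
- 0.234 / 0.15 = 1.56, so a barely significant result reaches 15% only if the control Week 8 mean is 1.56 or lower
- 0.33 / 0.15 = 2.20, so the planned difference reaches 15% only if that mean is 2.20 or lower

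**Step 3. How often they would disagree.** The documents give no Week 8 control mean, so a range is assumed. Eligible test teeth start at Schiff 2 or 3. Other assumptions: normal data, true difference 0.33, change SD 0.619, baseline mean 2.5 and SD 0.35, baseline-change correlation 0, -0.3 or -0.5. There were 60,000 simulated trials per cell.

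| Control mean, Week 8 | Significant, under 15%: t-test | Significant, under 15%: ANCOVA | Significant and at least 15%: t-test |
|---|---|---|---|
| 1.2 | 0.5-1.7% | 0.0-1.8% | 77.5-78.5% |
| 1.5 | 3.1-5.9% | 2.8-5.6% | 73.1-76.4% |
| 1.8 | 10.6-13.6% | 11.9-15.3% | 65.6-68.2% |
| 2.0 | 19.2-21.1% | 20.6-26.4% | 57.8-60.1% |
| 2.2 | 29.5-30.4% | 29.6-39.0% | 48.4-49.6% |

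A simpler calculation, taking 0.619 as the SD of the raw Week 8 score, gives 0.4% at 1.5, 18% at 2.0 and 29% at 2.2 (t-test).

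**Step 4. What the table measures.** It counts disagreement between the Schiff test and a threshold that the Section 2 rule does not use. A significant result of, say, 13% breaks nothing in the plan as written. It is a conflict only for a reader who first makes 15% the relevance criterion.

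**Step 5. Timepoint and sign.** Week 8 is the primary and secondary timepoint; Week 4 is exploratory (Protocol 10.2.4, SAP 4.6). The Table 14.2.1.2 shell marks Test versus Negative Control at Week 8 as the primary comparison. Its first footnote says a difference below zero is in favour of the product named first, and the programming note for the tactile table says the reverse sign is. Those notes describe the ANCOVA difference, but the percentage is formed in the same order, Test minus Control. An analyst would read the percentage correctly.

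**Step 6. Two measures.** Both Week 8 tests are specified, each at its own place in the hierarchy. The documents give no tactile SD or effect, so joint power can only be illustrated. With Schiff power 79.1% and tactile power assumed at 80%, it is 63%, 68% or 72% for correlations of 0, 0.5 or 0.8 between the test statistics. That bears on how likely the wider aim is to be met; it does not affect the validity of either test.

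**The case for a change.** The strongest case for a change is this. A success rule should be complete before unblinding. If relevance is a judgement, who makes it and on what basis can be fixed in advance at the cost of a few sentences. The sponsor calls the 15% a requirement, so treating it as decoration is hard to square with the text. If the control mean is near 2, about one trial in five would be significant and yet short of 15%.

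Part of this stands: clinical relevance is undefined, SAP Section 1 does not repeat it, and neither document says in so many words which 15% result counts.

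The rest does not carry to a change.

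- The one-in-five figure rests on an assumed control mean and on giving 15% a role the plan never gave it.
- Making 15% the criterion is a trade-off. At a true difference of 0.33 and a control mean of 2.0, the t-test chance of success would drop from 79% to 58-60%. With ANCOVA it would be about 58-63% at 2.0, but up to 89% at 1.2, so the price depends on a mean nobody has stated.
- The 15% comes from a guideline that the documents cite but do not reproduce. Whether it asks for both measures, a particular week or only a point estimate cannot be seen here, and it may contain its own pass rule. Writing one into the plan could misstate it.
- SAP Section 1 is a summary. SAP Section 5, which lists departures from the protocol's analysis, shows none to the success rule, so Section 2 of the protocol still governs.
- Saying that Schiff alone does not meet a two-measure aim only repeats what the primary and secondary hierarchy already shows.

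**Conclusion.** No change follows. The gap is an unwritten definition of clinical relevance, a judgement left to be made on the reported Schiff difference and its 95% confidence interval. The Schiff and tactile hypotheses, models, populations and timepoints are set, and no alpha or sample size depends on the missing definition. The power reproduces at 79.1% against the stated 80%.

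The 15% figure is a descriptive display for a regulatory guideline. Its Week 8 value against Negative Control can be read without ambiguity of sign, and an interval beside it would not alter any conclusion. The 0-39% range for significant-but-under-15% rests on assumed control means of 1.2 to 2.2 and assumed baseline variability and correlation. It would matter only if 15% were made a success criterion, which would be a debatable design choice and not a correction.

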#### 1.2.2 Study Design and Dose Rational

A randomized, examiner-blind, parallel group design is a recognized approach for providing evidence of the clinical effectiveness of a product in the reduction of DH [Holland, 1997]. In order to establish longitudinal performance, with the opportunity for benefit to be observed, an eight week treatment period will be used [Murray, 1994; Irwin, 1997; Ministry of Health (China), 2010].

In line with published recommendations [Holland, 1997] and the requirement of Chinese Ministry of Health guidelines [Ministry of Health (China), 2010] for the testing of functional dentifrices (desensitizing), two independent stimulus-based efficacy measures will be employed (tactile and evaporative air sensitivity) to evaluate the DH efficacy of the experimental dentifrice. A tactile stimulus will be administered using a constant pressure probe (Yeaple Probe [Polson, 1980]). An evaporative (air) stimulus will be administered using the Schiff sensitivity scale [Schiff, 1994].

One of the eligibility criteria at Screening in earlier DH studies was subject response to evaporative air sensitivity. In this study a qualifying response to a tactile stimulus will be included followed by a qualifying air blast on all teeth qualifying for tactile. At Screening and Baseline subjects will have a minimum of two teeth with a tactile score of  $\leq 20g$  and Schiff sensitivity score of  $\geq 2$ . To ensure consistent responders are entered into the study, the two test teeth selected at Baseline must be selected from those teeth eligible for both Schiff and tactile at Screening.

Orchardson & Collins tested 516 sensitive teeth and found that while around half were sensitive to both evaporative air and tactile stimuli, 33% were sensitive only to an evaporative air stimulus and 16% were sensitive only to a tactile probe [Orchardson, 1987]. Given that individual teeth may react differently to different stimuli it would be pragmatic to say the same for people. Therefore, some people may respond well to evaporative air sensitivity at Screening, but perhaps not to the same degree for tactile at Baseline, hence why both tactile

GlaxoSmithKline Consumer Healthcare Confidential Template Version Effective: 22-Jun-2017 Page **11** of **60** 

and evaporative air stimuli have been included at the Screening visit. This will help ensure that consistent responders to both stimuli are entered into the study, but will also enable more data to be gathered to understand the disparate response between the different stimuli that has been seen in previous studies.

Post-randomization, the two selected test teeth will be assessed using each of the clinical efficacy assessments. The selection of two 'test teeth' to evaluate changes in DH is common practice in sensitivity studies [Docimo, 2009]. The subjects will be stratified at the Baseline visit according to their maximum Schiff sensitivity score to enable the treatment groups to be balanced in terms of the subject's sensitivity severity.

The dosage regimen of twice daily treatment (morning and evening) brushing will be the same for all subjects, and has been selected based on widely recommended oral hygiene practice, and typical consumer habit.

According to ICH guidelines, for a study to be classed as truly double blind, not only does the examiner (and any appropriate member of staff who may be involved in the dispensing of products, analysis of data etc.) need to be blinded as to the treatment the subject receives, but the products under test must be identical in every way (color, flavor, appearance, packaging). Given it is almost impossible to ensure identical appearance, taste and packaging for the dentifrices evaluated in oral care studies, the level of blindness for this study is described as 'examiner blind' only.

Clinical trials evaluating clinical end points relating to pain can be prone to 'placebo effects' [Addy, 1985; West, 1997]. Such effects are frequently observed in dentine hypersensitivity studies. A study conducted to evaluate the natural history of the dentine hypersensitivity condition highlighted the existence of a 'no treatment' effect characterised by an improvement in sensitivity simply as a function of clinical study participation [Leight, 2008]. To help minimise the potential impact of such 'placebo' and 'no treatment' effects, an acclimatization period of 2-6 weeks will be included in this study from Screening, ahead of the Baseline assessments and randomization. During this period subjects will be provided with a toothbrush and a marketed, standard fluoride dentifrice to use in place of their regular oral hygiene products. Use of the acclimatization dentifrice will also help provide a standardised oral hygiene regimen prior to the Baseline visit. Subjects will brush twice daily, in line with recommended oral hygiene practice, and typical consumer habit, during this period.

The proposed examiners will be clinically qualified and will have been trained and have experience in the clinical assessments of DH, using both the Schiff sensitivity scale and a Yeaple probe. To minimize assessment variability, the same examiner will be responsible for a given clinical assessment from the Screening visit to the end of the study.

Complete information for this compound may be found in the single reference safety document (SRSD), which for this study is the Safety Statement.

GlaxoSmithKline Consumer Healthcare Confidential Template Version Effective: 22-Jun-2017 Page 12 of 60

Final 1.0 Clinical Protocol

